10.1 Assessment of Adverse Events

The Investigator is ultimately responsible for assessing and reporting all AEs as outlined in the protocol. The assessment and reporting of AEs may be delegated to a medically qualified sub-Investigator, trained on this study protocol, who is listed on the delegation of authority log. All AEs regardless of treatment group or suspected causal relationship to the study drug will be reported as described in this protocol.

Adverse events should be volunteered by the subject or solicited from the subject using a standard statement, obtained from examination of the subject at a site visit, or from observations of clinically significant laboratory values or special examination abnormal values. If an event assessed by one of the study scales requires intervention, or if in the opinion of the Investigator, it is clinically significant, then it will be reported as an AE.

All AEs are to be assessed and recorded in a timely manner and followed to resolution or until the Investigator determines that there is not an anticipated resolution. Each AE is to be documented with reference to severity, date of occurrence, duration, treatment and outcome. Furthermore, each AE is to be classified as being serious or non-serious. In addition, the Investigator must assess whether the AE is study drug-related or not.

10.1.1 Time Period for Collecting Adverse Events

Adverse event monitoring and reporting will begin after subjects sign the ICF, continue throughout the study and include EOS/ET/Follow-up. Subjects will be monitored by the study site staff for untoward effects and will be released from the study after the last procedure is completed and confirmed that the subject has no residual untoward effects from the study drug that may affect safety. Treatment-emergent AEs will be defined as events observed after starting administration of INDV-2000 or placebo. For Part III, run-in AEs will be defined as events observed after starting SUBOXONE SL film and before starting INDV-2000.

Surgical procedures, planned before enrolment of the subject in the study, are not considered AEs if the condition was known before study inclusion. In this case the medical condition is to be reported in the subject's medical history.

Any clinically significant symptoms will be reported as AEs. All AEs and corresponding treatment will be recorded in the eCRFs and a summary of all safety data will be presented in the final Clinical Study Report (CSR). Any ongoing AEs will be appropriately followed up until resolution or 14 days after EOS/ET. If findings are noted in the 90 day post last dosing day safety follow up call for male participants, these will be recorded as Adverse Events and followed until completion of required assessments. The study site personnel will make every effort to contact the subject as outlined in Section 6.6.2, after which the outcome of the AE will be considered ongoing and the subject will be noted in source as lost to follow-up.

If a subject experiences the onset of an SAE within 5 days following study completion and in the opinion of the Investigator, that SAE is associated with the study drug, it will be followed and reported as described in Section 11.2.

Confidential Page 56 of 108

If an SAE occurs that is deemed related to study drug, a PK sample will be taken as soon as possible after the event is reported. If possible, an additional sample should be collected when the SAE has been resolved.

10.1.2 Assessment of Intensity

The term "severe" is used to describe the intensity (severity) of a specific event (as in mild, moderate, or severe); the event itself, however, may be of relatively minor medical significance (such as a severe headache). This is not the same as "serious," which is based on subject/event outcome or action criteria usually associated with events that pose a threat to a subject's life or functioning. Seriousness (not severity) serves as a guide for defining regulatory reporting obligations.

Intensity	Definition	
Mild	Causes transient or mild discomfort; no limitation of usual activities; no	
	medical intervention required.	
Moderate	Causes mild to moderate limitation in activity; some limitation of usual	
	activities; no or minimal medical intervention or therapy is required.	
Severe	Causes marked limitation in activity; some assistance is usually required;	
	medical intervention or therapy is required; hospitalization is probable.	

An event existing prior to study drug administration and worsening in intensity post-study drug administration will be recorded as a new event. For events that occur after the first study drug administration, the maximum intensity, toxicity (Parts I and II only), and seriousness should be reflected in the event record.

Parts I and II only: For any applicable events appearing in the Toxicity Grading Scale considered by the Investigator to be an adverse event according to Section 10.1.4, the intensity of adverse events will be graded in accordance with the FDA Guidance for Industry: Toxicity Grading Scale for Healthy Adult and Adolescent Volunteers Enrolled in Preventive Vaccine Clinical Trials (Section 22.6, Appendix 6). Any event not falling under one of the specific categories listed will be graded as above.

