24 mg/6 mg of buprenorphine/naloxone. If run-in criteria are met, each subject will continue dosing with their stabilized dose of SUBOXONE SL film after the run-in period for required inclinic dosing. Qualifying subjects will continue to Day 1, where SUBOXONE SL film dosing alone continues for 2 more days. On Day 3, subjects will begin receiving doses of both SUBOXONE SL film and INDV-2000 for 7 days. Starting on Day 10, subjects will stop dosing with SUBOXONE SL film and dose with INDV-2000 alone for 4 more days and remain in clinic until completion of assessments on Day 14. Rescue medications to treat opioid withdrawal signs and symptoms will be allowed in the study based on Investigator's medical judgment. After assessments are completed on Day 14, subjects can begin a standard of care treatment for OUD. The EOS visit is scheduled for Day 21. If at any stage of the study a subject discontinues, they will be given options for their continued treatment for OUD by the clinical facility.

A schematic depicting the study design is in Figure 1.

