9 STUDY DRUG MANAGEMENT

9.1 Description

The term "study drug" is used throughout the protocol to describe INDV-2000, placebo and/or the SUBOXONE SL film received by the subject as per the protocol design. The term "IMP" is used throughout the protocol to refer to INDV-2000 and its placebo.

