14.9.1 Treatment-Emergent Adverse Events (TEAEs)

A TEAE is defined as an AE with start date/time at or after dosing with IMP. The number and percentage of subjects reporting TEAEs will be presented for each treatment by MedDRA system organ class (SOC) and preferred term (PT), each in descending order of frequency among all subjects in the given part of the study (then alphabetically in case of ties).

Incidence and number of study drug-related TEAEs, TESAEs, study drug-related TESAEs, TEAEs leading to death, TEAEs leading to IMP discontinuation, and TEAEs leading to IMP interruption will be presented both in an overall summary table and by SOC and PT. Included in the overall summary table will be incidence and number of severe TEAEs and TEAEs with grade 3 or higher toxicity grade (applicable for Parts I and II only). TEAE incidence will also be summarized by maximum severity within SOC and PT. Incidence of TEAEs will be summarized by PT only (not SOC) in descending order of incidence among all subjects (within study part).

In summaries by severity and relationship to study drug, if more than one TEAE is coded to the same PT for the same subject, the subject will be counted only once for that PT using the most severe/most related occurrence. Missing severity, toxicity, and relatedness will be queried until resolution.

Non-TEAEs and, for Part III, run-in AEs in the Run-In Safety Population will be summarized separately.

Separate listings will be presented for TEAEs, TESAEs, TEAEs leading to IMP interruption or discontinuation and TEAEs leading to death.

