### **5.5.2. Adverse Events**

A TEAE is an AE that started at or after first administration of IMP. A run-in AE is an AE that started at or after first administration of study drug during the run-in period. AEs will be assigned to study treatments based on start dates and times of treatments and start dates and times of AEs.

AEs will be coded to a System Organ Class (SOC) and Preferred Term (PT) using Medical Dictionary for Regulatory Activities (MedDRA). Additional details of the coding process, including the current version of the dictionary, are described in the Data Management Plan. All AEs will be listed for individual subjects. Listings will include SOC, PT, and reported term; treatment; onset date and time, end date, and duration; run-in status, treatment-emergence, severity, toxicity grade (though not required for Part III of the study), seriousness and seriousness criteria; relationship to study drug; action taken with IMP; action taken with SUBOXONE SL film; whether concomitant treatment was given; outcome; and whether the AE resulted in study discontinuation. Duration (days) is calculated as the AE end date – the AE onset date +1; for ongoing AEs, the date of end of study participation will be used as the end date. Duration will be missing if either the start or end date is partially or completely missing. SAEs, TEAEs leading to IMP discontinuation or interruption, AEs leading to SUBOXONE SL film discontinuation or interruption, and fatal AEs will be listed separately.

The incidence and number of all TEAEs, TESAEs, study drug-related TEAEs and TESAEs, severe TEAEs, TEAEs leading to IMP discontinuation or interruption, and fatal TEAEs will be presented in an overall summary table.

TEAEs, TESAEs, study drug-related TEAEs and TESAEs, and run-in AEs will be summarized by MedDRA SOC and PT, each in descending order of frequency among all subjects within study part (then alphabetically in case of ties). TEAEs will also be

summarized by maximum severity within SOC and PT. If an AE is reported more than once by a subject within a SOC and/or PT, the maximum reported level of severity will be used at each level of summation in the severity summary table.

Incidence and number of TEAEs will also be summarized by PT only (ie, not SOC), sorted by descending frequency among all subjects (within study part).

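### Part III: on the most direct reading, an adverse event that begins on SUBOXONE and worsens on INDV-2000 is not counted as treatment-emergent

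*Protocol*

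**What the plan says.** **Terms.** Protocol 9.1 defines study drug as "INDV-2000, placebo and/or the SUBOXONE SL film received by the subject as per the protocol design". It reserves IMP for INDV-2000 and its placebo, and SAP 5.1.5 notes that placebo does not apply in Part III.

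**Schedule.** Under protocol 4.1 and Appendix 3, SUBOXONE runs from Day -6 and is given alone through Day 2. Then: "On Day 3, subjects will begin receiving doses of both SUBOXONE SL film and INDV-2000 for 7 days". INDV-2000 continues alone on Days 10 to 13.

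**Recording.** Protocol 10.1.2 gives two rules. The first is "An event existing prior to study drug administration and worsening in intensity post-study drug administration will be recorded as a new event". The second concerns what each event's record must carry: "For events that occur after the first study drug administration, the maximum intensity, toxicity (Parts I and II only), and seriousness should be reflected".

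**Classification.** Protocol 14.9.1: "A TEAE is defined as an AE with start date/time at or after dosing with IMP". SAP 5.5.2: "A TEAE is an AE that started at or after first administration of IMP". SAP 5.5.2 also assigns each AE to a treatment by its start. Protocol 10.1.1 is worded differently: "Treatment-emergent AEs will be defined as events observed after starting administration of INDV-2000 or placebo", and for Part III "run-in AEs will be defined as events observed after starting SUBOXONE SL film and before starting INDV-2000".

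**Use.** Protocol 14.7.1 makes TEAE incidence, severity and relatedness, with serious, fatal and discontinuation events, the primary endpoint from first IMP dose. Under 14.7.2, Part III has no secondary endpoints.

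**The concern.** The worsening rule is tied to study drug, but the TEAE definition is tied to IMP. In Parts I and II the two start together, so nothing is lost. In Part III they are eight dosing days apart. An AE that begins in that gap falls after the first study drug dose, so its later peak is written into the existing record, and the start date in that record precedes IMP.

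Such an event would then be missing from the TEAE, severe TEAE, TESAE, relatedness and IMP-discontinuation summaries even if it became severe or serious on INDV-2000. By its start it would also be assigned to SUBOXONE. The error goes one way: on this reading the counts can only be too low. If staff read 10.1.2 differently, the same clinical course could be counted in one subject and not in another.

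The situation is foreseeable. Protocol 5.4 lets subjects proceed with a COWS score of up to 12, and SUBOXONE stops while INDV-2000 continues, so symptoms present early may be worse later.

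**Working it through.** The plan gives no figure to reproduce here. The check follows the definitions and then sizes the gap.

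**1. Apply the rules to test cases.** Take an AE that worsens on Day 11 and vary its onset. Use 10.1.2 for the record and 14.9.1 / SAP 5.5.2 for TEAE status.

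| Onset | Record under 10.1.2 (direct reading) | TEAE? |
|---|---|---|
| Day -10 (screening) | New event, start = day of worsening | Yes |
| Day -5 or -1 (run-in) | Same record, original start, maximum intensity | No |
| Day 1 or 2 (SUBOXONE alone) | Same record, original start, maximum intensity | No |
| Day 3 (after first INDV-2000) or Day 5 | Same record, start already on IMP | Yes |

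A complaint from screening that worsens on INDV-2000 is counted; one that began on SUBOXONE is not. At the edges, onset on Day -6 before the first film is outside the gap, and onset on Day 3 before the first INDV-2000 dose is inside it.

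**2. Where the excluded event goes.** Run-in onsets are run-in AEs. Onsets on Days 1-2 are run-in AEs under protocol 10.1.1, but SAP 5.5.2 classes them as neither treatment-emergent nor run-in. SAP 5.5.2 tabulates run-in AEs by SOC and PT, but plans the maximum-severity table for TEAEs only. Its separate listing for IMP discontinuation or interruption is likewise restricted to TEAEs, whereas the SUBOXONE counterpart takes all AEs.

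**3. Length of the gap.** There is no Day 0.
- Study-drug days: 6 (Days -6 to -1) + 13 (Days 1 to 13) = 19.
- Before first IMP: 6 + 2 = 8, and 8/19 = 42.1%.
- INDV-2000 days on which worsening can occur: 13 - 3 + 1 = 11, followed by follow-up.

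**4. Effect per subject.** One subject is 100/n percentage points. Part III enrols up to 16; the smaller sizes are illustrative.
- n = 16: 6.25
- n = 12: 8.3
- n = 8: 12.5

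This applies to overall TEAE incidence when the worsening is the subject's only event on INDV-2000. A subject with another TEAE leaves overall incidence unchanged, but can still shift severe TEAE or TESAE incidence by the same amount.

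**5. Chance that it arises.** The documents give no event rate, so p, the share of subjects with such a worsening, is an assumption. P(at least one) = 1 - (1 - p)^n:

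| p (assumed) | n = 16 | n = 8 |
|---|---|---|
| 2% | 1 - 0.98^16 = 27.6% | 14.9% |
| 5% | 1 - 0.95^16 = 56.0% | 33.7% |
| 10% | 1 - 0.90^16 = 81.5% | 57.0% |

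**The case against.** The strongest reply is that 10.1.2 can be read to capture these events. Its first rule contains neither *only* nor *first*, and INDV-2000 is itself a study drug, so an AE present on Day 2 did exist before a study drug administration and did worsen after it. Other text leans the same way. Section 10 treats intensification of an existing condition as an AE, 10.1 asks for a date of occurrence, and 10.1.1 speaks of events observed, not started, after INDV-2000. The CRF completion guidelines (protocol Section 16) are not among the documents and SAP 6.4.3.1 is redacted; either may settle the matter.

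This stands as evidence of ambiguity and is why confidence is medium. It does not close the gap, because none of these passages says that a worsening receives its own start date, and start date is what the TEAE definition uses. That the original start is kept is likewise an inference, though a natural one when maximum intensity goes into the event's record. SAP 6.6.5 deals with missing dates, not worsening.

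The second reply is that little is lost. Part III is open-label and descriptive. All AEs are listed with onset, severity, seriousness and action taken with IMP, and SAEs are listed separately. Reasons for study discontinuation are tabulated whatever the TEAE status. Laboratory, vital-sign and ECG changes are measured from the last value before IMP. The stopping criteria use AEs and SAEs. All of this stands and limits the harm to the summaries; detection and stopping are unaffected. It does not put the event back into the primary tables.

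Finally, 42% is a share of days, not a risk: an affected AE must also persist to Day 3 and then worsen. That is correct, and the figure should be read only as the width of the onset window.

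**Conclusion.** The concern holds and should be fixed, with medium confidence. Read directly, the recording and classification rules together keep out of the Part III primary TEAE tables any AE that starts after the first SUBOXONE dose and before the first INDV-2000 dose and then worsens on INDV-2000. Read otherwise, the count depends on who records the event. The number affected cannot be estimated from the documents; the effect is 6.25 points of incidence per affected subject at n = 16, under the conditions in step 4 of the working.

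The conclusion rests on two assumptions: that the original start date is kept, and that no unseen CRF guideline or redacted SAP text already supplies a rule. AEs that pre-date SUBOXONE and first worsen on INDV-2000, AEs that start on INDV-2000, and Parts I and II are not affected.

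**What to change.** First check whether the CRF completion guidelines or SAP 6.4.3.1 already contain a rule. If not:

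1. In protocol 10.1.2 and the CRF guideline, state that in Part III an AE ongoing at first INDV-2000 that then increases in intensity or becomes serious is closed and recorded as a new AE, starting at the date and time of worsening. The existing start-date definition then counts it once. Do not also add a worsening clause to the TEAE definition, which would create a second mechanism.
2. State the same recording rule in SAP 5.5.2, and align the wording of protocol 10.1.1 with 14.9.1.
3. For AEs already recorded without a worsening date, add one table of AEs with onset before first INDV-2000 that end on or after that date or are ongoing, by maximum severity and seriousness. It uses fields SAP 5.5.2 already lists. It will include AEs that never worsened or that peaked before IMP, so it is an upper bound on what the TEAE tables miss and should be labelled as such.

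**Cost.** The protocol wording needs an amendment with IRB approval (Section 17), plus a CRF guideline update. The SAP statement and the table need no protocol amendment and can proceed alone. Recording effort rises a little and TEAE counts may be slightly higher. No visits, samples or subjects are added, and no dose or clinical rule changes.

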10.1.3 Assessment of Causality

The Investigator or a medically qualified sub-Investigator, trained on this study protocol and listed on the delegation of authority log is responsible for determining the AE relationship to the study drug.

The following categories will be used to define the relationship of an AE to the administration of the study drug:

• Not Related: Data are available to identify a clear alternative cause for the AE other than the study drug.

Confidential Page 57 of 108

INDV-2000 Indivior Clinical Study Protocol: INDV-2000-102 09 May 2023

Related:

The cause of the AE is related to the study drug and cannot be reasonably explained by other factors (e.g., the subject's clinical state, concomitant therapy and/or other interventions).

A "reasonable possibility" is meant to convey that there are facts/evidence or arguments to suggest a causal relationship, rather than a relationship cannot be ruled out. The Investigator will use clinical judgment to determine the relationship. Alternative causes, such as natural history of the underlying diseases, concomitant therapy, other risk factors and the temporal relationship of the event to the study drug will be considered and investigated. The Investigator will also consult the IB in the determination of his/her assessment. For each AE/SAE the Investigator must document in the medical notes that he/she has reviewed the AE/SAE and has provided an assessment of causality.

There may be situations when an SAE has occurred, and the Investigator has minimal information to include in the initial report to Indivior or designated representative. However, it is imperative that the Investigator always make an assessment of causality for every event prior to the initial transmission of the SAE data to Indivior or designated representative. The Investigator may change his/her opinion of causality in light of follow-up information and amend the SAE data collection tool accordingly. The causality assessment is one of the criteria used when determining regulatory reporting requirements.

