6.5.1.2 Part I and II – Cohort Stopping Criteria

The study will be paused pending evaluation of all available data by the DRSC if any of the criteria listed below are fulfilled for an individual dosing cohort. The DRSC will conduct a review of unblinded data of the affected individuals to determine if any additional safety monitoring or changes to the protocol are required.

AEs:

- Three healthy volunteers experience a similar severe AE that is not clearly unrelated to the IMP, or
- Two healthy volunteers experience a similar SAE that is not clearly unrelated to the IMP.

Laboratory Abnormalities:

Two healthy volunteers with an abnormality of one or both of the following parameters, whose temporal relationship to the IMP makes causality plausible, confirmed on repeat testing:

- Serum ALT or AST >3 times the ULN.
- Total serum bilirubin >2 times the ULN (>35% direct bilirubin).

Vital Signs:

Two healthy volunteers fulfil one or both of the following vital sign criteria based on the mean of triplicate measures (≥1 minute apart), that will be completed once the first blood pressure reading is outside the accepted range:

- SBP <85 or >170 mmHg and/or change from Baseline >30 mmHg sustained for at least 1 hr (measures repeated every 15 min)
- DBP <45 or >105 mmHg and/or change from Baseline >30 mmHg sustained for at least 1 hr (measures repeated every 15 min)

ECG Criteria:

Two healthy volunteers fulfil the following ECG criteria based on the mean of triplicate measures (≥ 1 minute apart), that will be completed once the first ECG demonstrates a prolonged interval:

• QTcF ≥500 msec or uncorrected QT interval of >600 msec.

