11.2.2 Regulatory Reporting Requirements for Serious Adverse Events

Prompt receipt of notifications of SAEs to Indivior or designated representative from Investigators is essential in ensuring that legal obligations and ethical responsibilities regarding the safety of subjects are met.

Indivior has a legal responsibility to notify both the local regulatory authority and other regulatory agencies about the safety of the IMP. Indivior or designated representative will comply with country-specific regulatory requirements pertaining to safety reporting to Regulatory Authorities, IRBs and Investigators.

A suspected unexpected serious adverse reaction (SUSAR) is an SAE related to the IMP administered in any dose and that, in its nature or severity, is inconsistent with the IB. Indivior Pharmacovigilance will determine if an SAE meets the definition of a SUSAR and distribute SUSAR reports according to local regulatory requirements and Indivior policy. An Investigator who receives an Investigator safety report describing an SAE or other specific safety information (e.g., summary or line listing of SAEs, Dear Investigator Letter) will file it with the IB and will notify the IRB, if required according to local requirements.

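### The two causality categories in Protocol 10.1.3 are not complements: an adverse event with a reasonable but unconfirmed alternative cause fits neither, so the related-TEAE count rests on each investigator's own resolution

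*Protocol*

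**What the plan says.** Protocol 10.1 requires a binary call: "the Investigator must assess whether the AE is study drug-related or not". Protocol 10.1.3 supplies the two categories. The first is "Not Related: Data are available to identify a clear alternative cause for the AE other than the study drug". The second, *Related*, is "The cause of the AE is related to the study drug and cannot be reasonably explained by other factors".

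The next paragraph of 10.1.3 explains the phrase 'reasonable possibility' as meaning that "there are facts/evidence or arguments to suggest a causal relationship, rather than a relationship cannot be ruled out". Neither category uses the phrase. On how to decide, the section says "The Investigator will use clinical judgment to determine the relationship", and it lists matters to weigh, among them alternative causes and timing. It names no default category.

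Relatedness of TEAEs is part of the primary endpoint for all three parts (Protocol 3.1 and 14.7.1) and for Part III in the SAP (5.3.1). Related TEAEs and related TESAEs are tabulated separately (Protocol 14.9.1, SAP 5.5.2).

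The stopping criteria use different causality wording. In 6.5.1.2, for example: "Three healthy volunteers experience a similar severe AE that is not clearly unrelated to the IMP".

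**The concern.** A two-level scale works only if every event falls into exactly one level. Here each level has its own positive test, and neither is the negation of the other. Where an alternative explanation is reasonable but not clearly identified, the investigator must pick a category whose definition is not met.

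The surrounding text pulls both ways. The absence of a clear alternative cause keeps the event out of *Not Related*. The explanation of 'reasonable possibility' says that being unable to rule out a relationship is not enough, which pulls the event away from *Related*.

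At stake is the relatedness component of the primary endpoint. Two careful investigators could code the same event differently, and the tables would not show it. Part III is open-label with no concurrent control, so attribution there rests more heavily on the investigator's call.

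**Working it through.** **1. Are the two categories exhaustive?** Let C mean that data identify a clear alternative cause, and R mean that other factors could reasonably explain the event. From 10.1.3, *Not Related* requires C, and *Related* requires at least not-R. A clearly identified alternative cause is also a reasonable explanation, so C implies R. Three cases remain:

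| C | R | Category met |
|---|---|---|
| yes | yes | *Not Related* |
| no | no | *Related*, if the drug is judged the cause |
| no | yes | neither |

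The third row is the gap.

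**2. Can the third row occur?** Protocol 9.6.3.3 bars caffeine in Parts I and II from 24 hours before the Day -1 check-in until discharge from the unit. Take a headache on Day 2. Caffeine withdrawal is a reasonable explanation, so R holds and *Related* fails. Nothing collected need establish it as the clear cause, so C fails and so does *Not Related*.

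**3. Does another rule catch it?**
- Protocol 14.9.1 queries missing relatedness. SAP 6.6.5 imputes it as related if the query cannot be resolved. A gap event will carry a code, so neither rule is triggered.
- No section of either document gives a default for ambiguous causality.

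**4. Size.** The plan states no figure to reproduce: Protocol 14.2 gives no power basis and the analysis is descriptive. The number of gap events is not in the documents, so what follows is sensitivity only. If k subjects of n have a gap event as their only possibly related TEAE, related-TEAE incidence differs by k/n between the two ways of coding. The denominators come from Protocol 14.2.

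| Group | n | Step per subject (1/n) |
|---|---|---|
| Active, one cohort | 9 | 11.1 points |
| Placebo, two cohorts of one part | 6 | 16.7 points |
| Placebo, all four cohorts | 12 | 8.3 points |
| Part III at its maximum | 16 | 6.25 points |

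Both placebo rows are shown because Protocol 14.1 reports the parts separately but also combines placebo over cohorts.

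For Part III with an assumed k of 1 to 4: 1/16 = 6.25, 2/16 = 12.5, 3/16 = 18.75 and 4/16 = 25.0 points. As an illustration, if 4 subjects have a TEAE that plainly meets *Related* and 4 others have only gap events, incidence is 4/16 = 25.0% or 8/16 = 50.0%, depending only on coding.

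**The case against.** The best defence is that 10.1.3 leaves causality to a medically qualified investigator's judgment, as any causality scale must. The raters in Parts I and II are blinded, so any habit applies to active and placebo alike. Part III events are listed individually with their relationship, so a reader can inspect them. CRF completion guidelines exist (Protocol 16) but are not available here and may settle the matter.

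Part of this stands. Blinding limits differential coding between arms in Parts I and II, although it does not fix the level of the count. The listings allow inspection. But judgment applies criteria, and here the criteria leave the event unplaced. A guideline outside the protocol would not cure two protocol definitions that do not meet.

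A reader might infer more than the documents support:

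- *That nausea after SUBOXONE is stopped in Part III is a gap event.* Protocol 9.1 counts SUBOXONE SL film as study drug, and Protocol 10 lists study drug withdrawal among the conditions whose symptoms are adverse events. Such nausea has a study-drug explanation. It is not a clean example.
- *That unexpected serious reactions will be missed.* The SUSAR definition does turn on relatedness ("is an SAE related to the IMP administered in any dose"). However, every SAE goes to the sponsor within 24 hours (11.2.1), sponsor pharmacovigilance decides SUSAR status (11.2.2), and investigator causality is only one input to regulatory reporting (10.1.3). A missed report is possible but does not follow from the gap.
- *That differing site conventions drive the count.* The documents assign the call to the investigator or a trained sub-investigator and do not state the number of sites.
- *That the stopping criteria are wrong because their wording differs.* A wider net for pausing than for coding can be a deliberate protective choice. What the documents lack is a statement of how the two relate.
- *That related-TEAE incidence could swing by 50 points in Part III.* That needs 8 of 16 subjects with only gap events, for which the documents give no basis.

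**Conclusion.** The concern holds in a limited form. The two definitions in Protocol 10.1.3 leave a class of events in neither category, a binary answer is still demanded, and nothing else in the protocol or SAP closes the gap.

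Only the relatedness component is affected, that is, related TEAEs and related TESAEs. Overall TEAE incidence, severity, TESAEs, discontinuations and deaths are unchanged. There is no inference, so no error rate or power is involved.

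The logical gap rests on the text alone. Its numerical size rests on an assumed number of ambiguous subjects, and the 6.25 to 25 points for Part III is a sensitivity range, not a forecast. This should be corrected, because the defect lies in a stated rule behind a primary endpoint component and the remedy is a wording change.

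**What to change.** Rewrite the two categories in Protocol 10.1.3 as complements, using the standard the section already explains:

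- *Related*: there is a reasonable possibility that the study drug caused the event.
- *Not Related*: there is no such reasonable possibility.

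Keep alternative causes as matters to weigh, not as separate tests, and put the same wording in the CRF completion guidelines.

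The sponsor must also reconcile the causality wording of 10.1.3 with the 'not clearly unrelated' wording in 6.5.1.1 to 6.5.1.4, which differs from it. No stopping threshold or reading of those criteria is proposed here.

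The cost is a text change with no new data collection. The downside is that the related-TEAE count may move either way relative to current coding. Gap events now coded *Not Related* may become *Related* where evidence or argument points to the drug. Those now coded *Related* only because a link could not be excluded may become *Not Related*.
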